7.3 LOST TO FOLLOW-UP

A participant will be considered lost to follow-up if he or she fails to return for 2 scheduled visits and is unable to be contacted by the study site staff.

The following actions must be taken if a participant fails to return to the clinic for a required study visit:

- The site will attempt to contact the participant, reschedule the missed visit within 4 weeks, counsel the participant on the importance of maintaining the assigned visit schedule, and ascertain if the participant wishes to and/or should continue in the study.
- Before a participant is deemed lost to follow-up, the investigator or designee will make every effort to regain contact with the participant (where possible, 3 telephone calls and, if necessary, a certified letter to the participant's last known mailing address or local equivalent methods). These contact attempts should be documented in the participant's medical record or study file.
- Should the participant continue to be unreachable after two visit windows have passed, he or she will be considered to have withdrawn from the study with a primary reason of lost to follow-up.

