7 STUDY INTERVENTION DISCONTINUATION AND PARTICIPANT DISCONTINUATION/WITHDRAWAL

7.1 DISCONTINUATION OF STUDY INTERVENTION

If the participant is in the treatment phase of the trial, and he/she develops a treatment related CTCAE v5.0-defined adverse event grade 3 or above, the medication will be stopped and the participant assessed by the site study investigator who is a licensed physician/hepatologist. If the adverse event was severe, prolonged, or in the view of the investigator the participant is intolerant of the medication, the study drug will be stopped and the participant will no longer receive the study medication, but will continue to be followed in the study according to the protocol, in keeping with the "intention-to-treat" paradigm.

Participants will be monitored for drug induced liver injury and will use the scale below to grade the adverse effects*:

	Grade 1	Grade 2	Grade 3	Grade 4
ALT	BSL elevated: 3x BSL or >400 U/L	BSL elevated: >3-5x BSL	BSL elevated: >5 -20x BSL	BSL elevated: >20x BSL
AST	BSL nl:3 x ULN BSL elevated: 3x BSL	BSL nl:>3-5 x ULN BSL elevated: >3-5x BSL	BSL nl:>5-20 x ULN BSL elevated: >5-20x BSL	BSL nl:>20 x ULN BSL elevated: >20x BSL
Total Bilirubin	1.5 x ULN	>1.5-3.0 x ULN	>3.0-10.0 x ULN	>10.0 x ULN

Any participant found to meet the above criteria for grade 2 or higher drug induced liver injury will have the study medication stopped pending further study investigator evaluation.

In addition, participants will have the study medication stopped if **ANY** of the following occur[81]:

If normal baseline AST:

- AST value $>5 \times \text{ULN}$ in two repeat tests (within 14 days); OR
- AST value is $>8 \times \text{ULN}$; **OR**
- AST value $>5 \times \text{ULN}$ AND total bilirubin $>2 \times \text{ULN}^\ddagger$ OR presence of symptoms suggesting liver injury (severe fatigue, nausea, vomiting or right upper quadrant pain),

If elevated baseline AST or ALT:

- ALT or AST value $>3 \times \text{BSL}$ or 300 U/L in two repeat tests (within 14 days); OR
- ALT or AST value $>5 \times \text{BSL}$ or $>500 \text{ U/L}$ (whichever occurs first); OR
- ALT or AST value $>3 \times \text{BSL}$ or $>300 \text{ U/L}$ (whichever occurs first) AND total bilirubin $>2 \times \text{ULN}^\ddagger$ OR presence of symptoms suggesting liver injury (severe fatigue, nausea, vomiting, or right upper quadrant pain)

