8.1.4 FOLLOW-UP VISITS

Patients will return to the clinical center (see section 8.1.4.1 for optional remote visit allowances) for treatment phase follow-up visits at 4, 8, 12, and 24 weeks after randomization. Post-treatment phase visits will occur at week 28, week 36, and week 48 after randomization. Each visit will have an interval of time surrounding the ideal date for the visit during which the visit may be done and the data included in the trial database. The ideal date for a visit is the exact anniversary date from randomization. Visit windows will be constructed to be contiguous, so that at any point in time, some visit window is open, subject to a check on the minimum separation of at least two weeks is required between consecutive visits. The specific procedures to be completed at each of the follow-up visits are:

- **Week 4 visit:** Follow-up medical history including review of medications, adverse effects, and interim drinking history; review of study drug adherence; blood draw for fasting glucose and insulin, hepatic panel (total and direct bilirubin, AST, ALT, alkaline phosphatase, albumin, total protein); questionnaire for symptoms of NAFLD; focused physical examination including height, weight, waist and hip measurements, vital signs, oropharynx, and skin examination for petechiae or other signs of increased bleeding.
- **Week 8 visit:** Follow-up medical history including review of medications, adverse effects, and interim drinking history; review of study drug adherence; blood draw for fasting glucose and insulin, hepatic panel (total and direct bilirubin, AST, ALT, alkaline phosphatase, albumin, total protein); questionnaire for symptoms of NAFLD; focused physical examination including height, weight, waist and hip measurements, vital signs, oropharynx, and skin examination for petechiae or other signs of increased bleeding.

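### Section 7.3 can class an unreachable participant as withdrawn before week 24, and then requires no further attempt to obtain the primary ALT and gives no route back

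*Combined protocol and SAP*

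**What the plan says.** Section 7.3 defines a lost participant by two conditions together: one who "fails to return for 2 scheduled visits and is unable to be contacted by the study site staff". After any missed visit, "The site will attempt to contact the participant, reschedule the missed visit within 4 weeks", counsel the participant, and find out whether they wish to go on. Further effort comes next: "Before a participant is deemed lost to follow-up, the investigator or designee will make every effort to regain contact with the participant", by three phone calls if feasible and a certified letter if those fail, all documented. For someone the site still cannot reach, the rule is then: "after two visit windows have passed, he or she will be considered to have withdrawn from the study". Loss to follow-up is recorded as the main reason.

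Section 8.1.4 places "treatment phase follow-up visits at 4, 8, 12, and 24 weeks after randomization". It makes the visit windows contiguous but does not give their limits in weeks. Sections 9.2 and 9.4.2 take the primary endpoint from baseline and week 24 ALT only.

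Other relevant provisions:
- The schedule in Section 1.3 shows study drug dispensed once, at randomization.
- Section 7.2 does not replace participants who were randomized, received study drug and then left.
- Section 9.3 defines the intention-to-treat set as everyone randomized.
- Sections 9.2 and 9.4.1 allow for 10% missing primary data. Up to 10%, the analysis uses complete cases; above it, multiple imputation.

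**The concern.** A participant who goes silent early can still supply the primary endpoint, because week 4, 8 and 12 ALT values do not enter it. Going silent also need not mean being off treatment, since the full supply was handed over at randomization. Yet all the contact effort that Section 7.3 requires comes before the lost-to-follow-up status is assigned. Once it is assigned, no further attempt is required when week 24 arrives, and nothing says that someone who reappears goes back onto the visit schedule.

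At stake are the week 24 ALT of randomized participants who will not be replaced, and their week 28 to 48 data for the post-treatment secondary endpoints. If 10% or fewer are missing, these participants drop out of the primary analysis. Above 10%, someone who missed weeks 4 and 8 and was then classed as withdrawn has no post-baseline ALT from a scheduled visit to inform the imputation. People who go silent probably differ from those who stay, so the loss is probably not random.

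**Working it through.** **Step 1. When can the rule take effect?** Inputs are the visit weeks 4, 8, 12, 24 and 28 (Section 8.1.4) and the 4-week rescheduling limit (Section 7.3). The protocol gives no window limits, so two readings are tried, both assumptions.

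- *Midpoint windows.* Boundaries are (4+8)/2 = 6, (8+12)/2 = 10, (12+24)/2 = 18 and (24+28)/2 = 26. The week 8 window closes at week 10 and the week 12 window at week 18; the week 24 window runs from 18 to 26.
- *Rescheduling limit.* Adding 4 weeks to the ideal date of the second missed visit gives 8+4 = 12 or 12+4 = 16.

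| Visits missed | Midpoint reading | Weeks before week 24 | Rescheduling reading | Weeks before week 24 |
|---|---|---|---|---|
| 4 and 8 | week 10 | 14 | week 12 | 12 |
| 8 and 12 (or 4 and 12) | week 18 | 6 | week 16 | 8 |

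Every entry falls before week 24, so the conclusion does not depend on which reading is used. The pair 4 and 12 is included because Section 7.3 does not say whether the two visits must be consecutive.

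**Step 2. Reproduce the plan's sample size.** Inputs from Section 9.2: difference δ = 20 points, SD σ = 31, power 90%, 10% missing, Williams' test with three doses and placebo. The upper 5% Williams critical value, simulated with 1,000,000 draws at large degrees of freedom, is c = 1.737.

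n = 2[σ(c + z₀.₉₀)/δ]² = 2[31 × (1.737 + 1.282)/20]² ≈ 43.8, rounded up to 44. Then 44/0.90 = 48.9, so 49 per group against the stated 50. The other five rows of the table in Section 9.2 also come within 2 per group. (The upper 2.5% value, 2.030, gives 59 per group, so the stated size matches the one-sided 5% value. That is a separate matter, and is noted here only to show which critical value the power figures use.)

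**Step 3. What does extra loss cost in power?** With 50 randomized per group and complete cases, n = 50(1 − m) for missing fraction m, and power = Φ(δ/[σ√(2/n)] − c).

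- m = 10%: n = 45, Φ(3.060 − 1.737) = 90.7%
- m = 15%: n = 42.5, Φ(2.974 − 1.737) = 89.2%
- m = 20%: n = 40, Φ(2.885 − 1.737) = 87.5%

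The allowance is 10% of 200 = 20 participants. Ten further losses (5% of 200) would lower power by 90.7 − 89.2 = 1.5 percentage points. The documents give no expected number of participants who would meet the lost-to-follow-up rule.

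**The case against.** Four stronger readings are tempting, and the documents do not support them.

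- *Two missed visits remove a participant.* They do not. The participant must also be unreachable after documented efforts; one who can be reached is not lost under Section 7.3.
- *Participants are closed out and barred from week 24.* The text says they are considered withdrawn. It does not forbid later contact, and the closeout form appears only at the last visit. The defect is that nothing requires a further attempt or provides for return.
- *The rule treats early absentees worse than those who stop study drug.* Section 7.1 says of the latter "but will continue to be followed in the study according to the protocol", but they are people the site can still contact, so the comparison is not like for like.
- *A sizeable part of the missing-data allowance is used up.* No rate in the documents supports this.

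There are also real safeguards. Section 8.1.4.1 lets the week 4 and 8 visits be done wholly or partly by telemedicine, with outside laboratories, so missing both and being unreachable should be uncommon. The early visits also serve liver-injury and bleeding surveillance, so it matters when they are missed. Under midpoint windows, the weeks 8 and 12 case is decided just as the week 24 window opens, so an attempt at that exact moment would add little.

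All of this stands, and it limits the size of the problem. It does not fill the gap: an unreachable participant can acquire withdrawn status weeks before the primary visit, with no required attempt afterwards.

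**Conclusion.** The point holds as a cheap improvement. Applied as written, Section 7.3 can assign lost-to-follow-up withdrawal 6 to 14 weeks before week 24 under the two window readings tried, without requiring an attempt at the primary ALT or stating that a returning participant resumes visits. The exact weeks rest on assumed window limits; that they precede week 24 holds under both readings. The affected group is probably small, and power moves only from about 90.7% to 89.2% if missing data rise from 10% to 15%. The case for change therefore rests less on power than on avoiding a loss of the primary value that is probably related to outcome. How related it is, and how many silent participants would return, cannot be judged from the documents.

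**What to change.** Amend Section 7.3 as follows:

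1. Do not make lost-to-follow-up status final until the week 24 window has closed, nor final study status until the week 48 window has closed. Until then, use an interim 'inactive' status.
2. Require one further documented contact attempt within the week 24 window, in addition to those already made, for anyone who has not withdrawn consent or been withdrawn by the investigator under Section 7.2. Aim at least for the hepatic panel, keeping the same-laboratory requirement for ALT in Section 8.2.
3. State that a re-contacted participant resumes the remaining scheduled visits. Any decision on study drug stays with the existing protocol rules.
4. Say whether the two missed visits must be consecutive.

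The cost is protocol wording, one status in the data system and a few extra contact attempts. No visits or procedures are added.

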8 STUDY ASSESSMENTS AND PROCEDURES

8.1 EFFICACY ASSESSMENTS

8.1.1 VISIT SCHEDULE OVERVIEW

- Screening for eligibility for randomization (60 days)
- Randomization to treatment (1 visit)
- Treatment phase (4 visits over 24 weeks)
- Post-treatment phase (3 visits over 24 weeks)

8.1.2 SCREENING AND BASELINE DATA COLLECTION

Patients who appear to be eligible after chart review will be invited to undergo screening. Recording of screening data on NASH CRN forms may not start until the patient has signed the consent statement. Screening and baseline data collection procedures detailed below will include questionnaires, baseline medical history, cardiovascular risk factor assessment, physical examination, measurement of fasting serum glucose and insulin, lipid and metabolic tests, etiologic tests, FibroScan® VCTE exam, and blood collection for serum and plasma banking. Prior therapy for NAFLD will be reviewed as outlined in the inclusion and exclusion criteria. Patient charts will be reviewed for historical information.

All participants who sign the consent documents will be registered in the trial database. Each participant who starts screening will be accounted for at the end of screening, as either a screening success (enrolling in the trial) or a screening failure. A screening failure is defined as a participant who signed the consent form, but is found to be ineligible prior to randomization. Screening failures include patients who meet medical eligibility criteria but who refuse randomization in the trial. Reasons for screening failure will be recorded in the trial database. Screening data collection will be conducted over two clinic visits usually completed on separate calendar days. The goal of the first screening visit is to obtain consent and record data regarding the trial's inclusion and exclusion criteria; the goal of the second screening visit is to complete collection of baseline data on patients who appear eligible. This separation of procedures between two visits is provided as a practical

guideline. Screening procedures and data collection can be organized as appropriate at each clinical center. The procedures completed during screening are described below.

Screening visits

Determination of eligibility will be based mostly on chart review of standard of care tests and procedures that were completed before the first screening visit. The participant will sign the consent at the first screening visit (or before) to obtain any tests and procedures needed to finalize eligibility after chart review. Participants will undergo a medical history and detailed physical examination including anthropometric assessments (body weight [kg], body height [m], body mass index [BMI], waist circumference [cm], and hip circumference [cm]) to identify other illnesses and contraindications for participation, including signs of bleeding (gum, petechiae), hepatosplenomegaly, peripheral manifestations of liver disease, and ascites. Laboratory test results that need to be recorded from chart review or obtained as part of the screening visits include: tests for hepatitis B (HBsAg) and hepatitis C, anti-nuclear antibody (ANA), anti-mitochondrial antibody (AMA), anti-smooth muscle antibody (ASMA), ceruloplasmin, A1AT concentration, iron overload (iron, TIBC, and ferritin) and thyroid stimulating hormone (TSH). The ALT measurement must be completed within 30 days of randomization. The additional lab tests for screening must be completed within 60 days of randomization: fasting serum glucose, insulin, HgbA1C, complete blood count (CBC) with white blood cell differential, hepatic panel (total and direct bilirubin, AST, alkaline phosphatase, albumin, total protein, GGT), coagulation tests (aPTT, PT, INR), metabolic panel (sodium, potassium, chloride, carbon dioxide, calcium, BUN, creatinine, uric acid), eGFR (using the CKD-EPI equation), C-reactive protein, and lipid panel (total cholesterol, triglyceride, LDL, HDL), PSA (males only). Use of medications that could potentially interact with vitamin E (e.g. anticoagulants, those altering fat absorption) will be queried and documented.

Females of childbearing potential must have a negative pregnancy test and will be assessed for willingness to use ≥ 1 form(s) of effective birth control for the duration of the study. Frequency and amount of alcohol intake will be obtained using the Skinner Questionnaire and the Alcohol Use Disorders Identification Test (AUDIT). Patients will complete the BEV-Q questionnaire to document habitual beverage intake (grams, energy) and a liver symptoms questionnaire developed by the NASH CRN to identify symptoms associated with liver disease, severity of symptoms, and impact on lifestyle. A blood sample will be drawn to obtain serum/plasma for banking for future analysis of markers of exploratory endpoints including measures of vitamin E.

Baseline FibroScan®

A FibroScan® procedure will be performed within 60 days of randomization for baseline data collection purposes. Before the procedure, the patient will verify that he/she has fasted for 3 hours prior to the exam. The FibroScan® exam will be performed by a FibroScan®-certified technician. Duration of the exam will be no longer than 30 minutes.

The NASH CRN clinic data system will include coding to check patient eligibility based on keyed data forms. The randomization visit will only become available in the data system when all forms are keyed, and any issues will be flagged as red until resolved or verified, so clinic staff can use the data system to visually identify the items that still need to be completed, keyed, or verified after data from the screening visit are keyed. The randomization visit should not take place until the data system indicates that the patient is eligible except for the items that can be completed only at the randomization visit.

8.1.3 RANDOMIZATION

The randomization visit is the visit at which randomization takes place and the patient is issued the study medication randomly assigned to the patient. Randomization is the act of generating the random study medication assignment and is the procedure which defines a patient's enrollment into the trial. Randomization can only occur after eligibility has been fully checked and all data collected at the screening visits have been keyed to the trial database. Since these processes take time, randomization cannot be done at a screening visit, and since study medication needs to be issued to the patient, the randomization visit must be completed in person with the patient. Therefore, a visit separate from the screening visit is necessary. Since this will be a visit on a different calendar day and the study medication will be prescribed at this visit, good clinical practice requires that a few basic checks of the patient's well-being be completed at the randomization visit.

The procedures completed at the randomization visit are: verification that the patient is feeling well; affirmation of consent; review of concomitant drugs and vital signs (systolic and diastolic blood pressure, heart rate, respiratory rate, body temperature). All patients will be given information on a healthy life style and diet appropriate for their weight and other factors.

Generation of the random treatment assignment will occur at this visit. The randomization process includes the same electronic check on eligibility that the staff may run prior to the randomization visit. The medication assignment will not be generated unless the check finds that the patient is eligible, and the clinic staff indicates that they want to randomize the patient. The random treatment assignment will consist of medication 'kit' numbers; these numbers will be unique and will be specific to the particular patient it was generated for. They will correspond to numbered cartons ('kit') of medications which have been sent to the clinical center's research pharmacy (or clinical coordinator if not using a pharmacy) by the Drug Distribution Center. The research pharmacy (or clinical coordinator) will issue the specific numbered kit to the patient. Each patient's random treatment assignment will be generated for that specific patient and will not be transferable to another patient. Once the assignment has been generated, the patient should be issued the assigned study drug and instructed about starting the drug and monitoring for adverse effects. The date of randomization is the 0 time for reckoning all follow-up visits (i.e., all follow-up visits are scheduled at specific times measured from the date of randomization). The data system will display a personalized appointment schedule for the patient; this schedule will indicate the ideal date for each follow-up visit, as well as the time window around the ideal date during which the follow-up visit may be done. This will ensure that the data collected at the follow-up visit may be used in the trial.

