5.2 EXCLUSION CRITERIA

Patients who satisfy any of the following exclusion criteria will be ineligible for randomization:

- Concurrent or prior use (within 90 days) of vitamin E supplements in excess of 40 IU/day
- Current or history of significant alcohol consumption for a period of more than 3 consecutive months within 1 year prior to screening (significant alcohol consumption is defined as more than 20 g/day (~1.5 drinks/day) (> 10.5 drinks per week) in females and more than 30 g/day (~2 drinks/day) (> 14 drinks per week) in males, respectively. One "standard" drink (or one alcoholic drink equivalent) contains roughly 14 grams of pure alcohol, which is found in: 12 ounces of regular beer, 5 ounces of wine, or 1.5 ounces of distilled spirits).
- Inability to reliably quantify alcohol consumption based upon local study physician judgment
- Continued use of drugs historically associated with NAFLD (amiodarone, methotrexate, systemic glucocorticoids, tetracyclines, tamoxifen, estrogens at doses greater than those used for hormone replacement, anabolic steroids, valproic acid, and other known hepatotoxins) for more than 2 weeks in the 6 months prior to randomization
- Current use of anticoagulation therapy (not including antiplatelet agents such as aspirin or clopidogrel)
- Platelet count below 150,000 /mm³ within 90 days of randomization
- History of condition(s) that cause increased risk of bleeding, including hemophilia A, hemophilia B, von Willebrand disease, or other clotting factor deficiencies.
- Prior or planned (during the study period) bariatric surgery (eg, gastroplasty, Roux-en-Y gastric bypass)
- Uncontrolled diabetes defined as HbA1c 9.5% or higher within 60 days prior to randomization
- Clinical evidence of hepatic decompensation as defined by the presence of any of the following abnormalities:
 - Serum albumin less than 3.2 g/dL
 - International Normalized Ratio (INR) greater than 1.3
 - Direct bilirubin greater than 1.0 mg/dL

- History of esophageal varices, ascites or hepatic encephalopathy
- Evidence of other forms of chronic liver disease:
 - Hepatitis B as defined by presence of hepatitis B surface antigen (HBsAg)

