 - Evidence of recent or current hepatitis C as marked by the presence of anti HCV antibody with detectable HCV RNA in serum within 1 year prior to enrollment. Participants with anti HCV antibody positivity who have undetectable HCV RNA at least 1 year prior to enrollment (either due to spontaneous clearance or clearance with treatment) will be eligible to participate if HCV RNA at entry remains undetected
 - Evidence of ongoing autoimmune liver disease as defined by compatible liver histology
 - Primary biliary cirrhosis as defined by the presence of at least 2 of these criteria
 - (i) Biochemical evidence of cholestasis based mainly on alkaline phosphatase elevation
 - (ii) Presence of anti-mitochondrial antibody (AMA)
 - (iii) Histologic evidence of nonsuppurative destructive cholangitis and destruction of interlobular bile ducts[1]
 - Primary sclerosing cholangitis
 - Known history of Wilson disease, alpha-1-antitrypsin liver disease, or hemochromatosis. Any other type of liver disease that is currently active other than NASH such as drug-induced liver disease, liver cancer, or bile duct obstruction.
- Serum alanine aminotransferase (ALT) greater than 400 U/L within 90 days of randomization
- Moderate or severe renal impairment (serum creatinine ≥ 2.0 mg/dL or eGFR < 60 mL/1.73m²)
- History of biliary diversion or evidence of current biliary obstruction
- Known positivity for Human Immunodeficiency Virus (HIV) infection
- Active, serious medical disease with likely life expectancy less than 5 years
- Active substance abuse including inhaled or injection drugs in the year prior to screening
- Pregnancy, planned pregnancy, potential for pregnancy and unwillingness to use ≥ 1 effective form(s) of birth control during the trial, breast feeding
- Current use of medications that may impact the absorption of fat-soluble vitamins (i.e. orlistat or cholestyramine)
- Pre-existing history of fat malabsorption
- Males at high risk of prostate cancer, including:
 - PSA >ULN at baseline
 - History of prostate cancer
 - Age 45 or older with a first-degree relative (father or brother) diagnosed with prostate cancer at an early age (younger than age 65).
 - Age 40 or older with more than one first-degree relative who had prostate cancer at an early age (younger than age 65)
- Participation in an IND trial in the 30 days before randomization

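### Pregnancy bars randomization, but the only listed pre-dose pregnancy test is at screening, has no time window, and is not repeated at the visit where drug is issued

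*Combined protocol and SAP*

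**What the plan says.** Section 5.2 opens with "Patients who satisfy any of the following exclusion criteria will be ineligible for randomization" and includes "Pregnancy, planned pregnancy, potential for pregnancy and unwillingness to use ≥ 1 effective form(s) of birth control during the trial, breast feeding". The status that counts is therefore the status at randomization.

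Section 8.1.2 places the test in screening: "Females of childbearing potential must have a negative pregnancy test and will be assessed for willingness to use" at least one effective contraceptive method. No date limit accompanies that sentence. The same section does date other tests. For ALT it says "The ALT measurement must be completed within 30 days of randomization". For a named set of other laboratory tests it says "The additional lab tests for screening must be completed within 60 days of randomization". The pregnancy test is in neither group.

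Section 8.1.3 makes randomization a separate visit, in person, on a different calendar day from screening, and this is where the numbered kit is handed over. Its content is given as "The procedures completed at the randomization visit are: verification that the patient is feeling well; affirmation of consent; review of concomitant drugs", followed by vital signs. The kit is released by the same electronic eligibility check that staff can run before the visit.

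Section 8.1.4 lists the next pregnancy test at week 24, the end of treatment. The week 4, 8 and 12 visits list none. The amendment history (section 10.4) records that the week 24 test was added at the request of the data and safety monitoring board.

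**The concern.** Pregnancy status can change in the interval between screening and randomization. Several slower-moving criteria have explicit windows in sections 5.1 and 5.2: ALT 30 days, CAP 60 days, HbA1c 60 days, platelets 90 days. The pregnancy test has none and is not refreshed when drug is dispensed. A site that follows the plan exactly could give study drug to a woman who meets an exclusion criterion that day.

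What is at stake is participant safety and clean eligibility. Under sections 6.3 and 8.3.9, a pregnancy found on study means that drug is stopped, the code may be broken, and the participant is told of teratogenic risk. Section 7.2 lets the investigator withdraw her, and a participant withdrawn after receiving drug is not replaced. A test on the day of dispensing would avoid those steps for a pregnancy detectable by then.

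**Working it through.** The plan gives no figure to reproduce, and alpha, power, effect size and sample size are not involved. The check sets the relevant sections side by side.

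1. **Where tests are scheduled.** The pregnancy row of the data collection schedule (section 1.3) lost some columns in the text available for this review. It shows two marks, with three empty cells after the second. The last three columns are weeks 28, 36 and 48, so the second mark falls at week 24 and the first is read as screening. The visit text agrees: section 8.1.2 has the test at screening, section 8.1.4 has it at week 24, and section 8.1.3 has none. The reading can be confirmed on an intact copy of the table.

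2. **Where drug is dispensed.** The schedule marks drug dispensing at the randomization visit only.

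3. **Age of the test at dispensing.** No maximum is stated, so it has to be inferred.
   - Lower end: randomization cannot take place at a screening visit and falls on a different day, so at least 1 day.
   - Upper end: the synopsis and section 8.1.1 set a 60-day screening phase. Section 5.4 allows one rescreening when registration to randomization exceeds 60 days. Together these imply about 60 days. This bound is indirect: neither place mentions the pregnancy test, and rescreening is permitted rather than required.
   - Assumption: the test is done within the screening phase. Result: 1 to about 60 days.

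4. **After the fix.** With a test at the randomization visit, the age at dispensing is 0 days, a reduction of 1 to about 60 days. The interval from randomization to the week 24 test is 24 × 7 = 168 days and does not change.

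5. **What the eligibility check can see.** It works on keyed data. With no pregnancy test listed at the randomization visit, the result it uses is the screening one.

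No expected number of pregnancies is given, because the documents contain no figures from which to derive one.

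**The case against.** The strongest reply is that this is a consistent design choice. Planned pregnancy and unwillingness to use contraception are exclusions, willingness is assessed at screening, and section 8.3.9 requires precautions. The plan relies on the same approach, with medical history at weeks 4, 8 and 12, for the 168 days to week 24. A gap of up to about 60 days is also the window accepted for other eligibility laboratory tests, such as INR and HbA1c. Section 2.3.1 reports no significant adult toxicity at the top dose and lists no reproductive risk; teratogenicity appears only in the notification sentences of sections 6.3 and 8.3.9. Much of this stands: the risk is residual and its size is unknown. But willingness to use contraception does not verify status on the day, and pregnancy is an exclusion that applies at randomization.

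Three stronger readings are tempting and are not supported.

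- A reader might infer that a chart result of any age is acceptable, because section 8.1.2 says of results that predate screening: "Determination of eligibility will be based mostly on chart review of standard of care tests and procedures that were completed before". Pregnancy is not among the chart-review tests named there, and the screening-phase and rescreening provisions point to about 60 days.
- A reader might cite the 0 mL at randomization in the blood-draw table (section 10.2.1). That table has no pregnancy-test row for any visit, including screening and week 24, where the test is required. It shows nothing either way.
- A reader might call the randomization visit the only point at which a test could prevent dispensing. Section 8.1.2 lets sites arrange screening procedures, so a late screening test or a stated maximum age would also narrow the gap.

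**Conclusion.** The point holds as a minor one. The listed procedures leave an interval of 1 to about 60 days before first dosing in which a conception would go undetected, although pregnancy bars randomization. The range assumes that the test is done within the 60-day screening phase; no document states that limit for this test. The conclusion also rests on reading the damaged schedule row as screening and week 24, which the visit descriptions support.

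The documents do not establish the size of any fetal harm, and none is claimed. The sample size, the Williams' test and the primary result are unaffected. The case for acting is that the remedy is cheap and fits a visit at which section 8.1.3 already calls for basic checks because drug is being issued.

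**What to change.** Require a negative urine pregnancy test for women of childbearing potential at the randomization visit, before the kit is issued. Either move the screening test to that visit or repeat it there. Add the test to the randomization column of the schedule in section 1.3, to the procedure list in section 8.1.3, and to the electronic eligibility check. Section 8.1.2 already allows for eligibility items that can be completed only at that visit. A stated maximum age for the screening test would be a weaker alternative: it would shorten the gap without closing it.

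The cost is at most one extra urine test per woman of childbearing potential at an existing in-person visit, no added blood, one data field and a minor amendment. If the test is moved rather than repeated, there is no extra test, but a pregnancy is found later, after other screening work has been done. A very early pregnancy can still be missed.
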